### **1.3.3 Analysis Datasets**

#### **1.3.3.1 Intent-to-Treat**

Linear mixed-effects models provide unbiased estimates of effects even in the presence of missing data provided that the data may be assumed to be missing at random. All available data (to the last time point of interest – possibly 2 or 3 years due to limited follow-up beyond that time). The data will be examined for evidence of informed missingness.

#### **1.3.3.2 Per Protocol dataset**

These are observational, retrospective data and therefore per protocol is not well defined. As above, the data will be examined to determine whether characteristics are different between those who are present or absent at the various follow-up time points.

### **1.3.4 Additional Statistical Considerations**

#### **1.3.4.1 Missing, Unused or Spurious Data**

Differences in the characteristics of populations with follow-up versus those without should be described. The effect of missing descriptive data on the population characteristics should be estimated.

#### **1.3.4.2 Planned Interim Analysis**

Not applicable.

#### **1.3.4.3 Criteria for Termination of the Clinical Investigation**

Not applicable.

#### **1.3.4.4 Additional Statistical Analyses**

Additional analyses (using some or all variables described in section 1.1) will include:

- McNemar's test for a change in proportions over time in paired categorical variables.
- Fisher's exact tests will be used to look for associations between age group and other categorical variables.

### **1.3.5 Conduct of Statistical Analysis**

██████████ will conduct the analysis. ██████████ will advise and discuss the approaches and provide domain knowledge.

R software will be used to analyse the data (versions of base and extension packages will be noted).

### **1.3.6 Quality control on statistical analysis**

██████████ will conduct quality control on the R code used, and the summarised data.

### **1.3.7 Presentation of data**

The report will conform to a conventional format with a number of data completeness and population summaries (such as demographics).

For the age groupings, ABS age ranges will be utilised unless sample sizes are too small. In this situation, one or more groups will be combined. While quintiles were of interest the age breakpoints were not useful and not considered further.

For all linear and linear mixed-effects models, estimates of the marginal means and plots of change over time will be presented. P-values for interaction effects and differences between groups (where relevant because of significance or interaction or main effects) will be presented. For logistic models estimated odds ratios and p-values will be presented.

Tables of summaries at each time point will be presented for the overall cohort as well as for those present or absent at a subsequent time point. Tables of cross-tabulations will also be presented.

## 2 DEVICE CHOICE BY AUDIOLOGICAL PROFILE

### 2.1 Overall objectives

The aim is a description of the characteristics of patients using different implantable hearing solutions provided by Cochlear. Primarily we wish to compare audiological configurations across device types, and within types if feasible numbers. Measures are:

- Audiometry air-conduction thresholds
- Audiometric bone-conduction thresholds
- Degree of hearing loss
- Etiology
- Use of hearing aids
- Duration of HL
- Age

Air (AC) and bone conduction (BC) thresholds will be used to indicate “sensorineural” (SN) and “conductive” (CO) components of HL. BC thresholds indicate the sensorineural HL component. The air-bone gap or difference AC-BC indicate the conductive component.

Etiology should correspond to particular SN and CO mappings. Similarly, the technical specifications of each device type can be mapped to SN and CO values based on transducer power and other factors (see Hypothesis).

The secondary objective is to characterise the baseline SSQ and HUI3 total scores across device types. In addition, telephone use, presence of tinnitus, and dizziness may be different across device types.

### 2.2 Study population

All available baseline data will be used. Firstly, the devices will to be combined into device types as below. The larger **overall** groups are defined as below.

#### **BAHA**

Baha Connect: BI210, BI300, BIA400

Baha Attract : BIM400

#### **AMEI**

Codacs : Codacs (DI110)

MEI : Carina (MET7000), Met (MET1000)

**CI**

Contour : CI512, CI513, CI612, Freedom CI24RE(CA) (CI24RECA), 24 Contour (CI24RC), 24 Contour Advance (CI24RCA)

Straight : CI422, CI522, CI622

Modiolar : CI532, CI632

Other : CI24RE(ST) (CI24REST), CI24RST (CI24RST), CI24REH (Hybrid L), CI other

**ABI**

ABI : ABI541

Bilaterally implanted patients can be simply divided into CI-CI and Baha-Baha, and any other combination for numbers. If sufficient (i.e.  $N > 30$ ), CI-CI can be treated as a separate group, etc.

**2.3 Statistics****2.3.1 Sample Size**

There are a total of 1361 baseline records available in the IROS database, with 1192 with some exploitable threshold data (BC value or HL degree category missing for 50 Baha and 115 CI). There are approximately 247 of the total set with BC data, of which 84 are CI. Thus, most of the CI group have HL degree but no specific AC or BC data. The exploitable AC and BC data will be used to provide individual data points. The HL degree data for CI can be summarised in terms of a range of values.

It is known that BC thresholds above ~80 dB HL cannot be measured due to transducer saturation. When this occurs often an AC threshold alone is given, but these are generally of high values.

**2.3.2 Analyses**

The primary aim is a description of the characteristics. No formal hypothesis testing will be performed.

[figure not shown]
**2.3.2.1 Pass/Fail Criteria**

NA.

### 2.3.2.2 Primary Hypothesis

A schema originally produced by ██████████ serves as a reference for the design specifications of different Cochlear hearing solutions in terms of what level of SN and CO HL components may be addressed (Figure below).

We hypothesise that the SN and CO values in the IROS database should match those for the device labelled in the figure. We do not have a good handle on Hybrid HL in IROS database at present. We see that a mapping area for conventional acoustic hearing aids (HA) is indicated (yellow). Generally speaking, HAs can provide up to 60 dB corrective gain. Approximately half of the SN HL needs to be corrected and all of the CO HL needs to be corrected. Acoustic implants such as Carina and Codacs (DACs) bypass much of the the CO HL, as do Baha devices. However, Baha devices are more limited in corrective gain for SN HL (~30 dB).

To answer the hypothesis a new device type mapping will be created from current fitting ranges. Then the ipsilateral SN and CO values from IROS will be plotted onto the schema with specific point and colour types each device type (or overall device type).

### 2.3.2.3 Secondary Hypotheses

Summarise of the characteristics of patients using each device type will be made. Such as the etiology and demographics, and also baseline SSQ and HUI3 scores.

## 3 IMPLANTABLE HEARING SOLUTION UTILITY GAIN

Not currently applicable.

## 4 FACTORS INFLUENCING QOL OUTCOMES WITH CI

To differentiate from previous publication the approach will be to establish odds of improvement in HUI Mk III scores. The minimum clinically important change/difference in HUI3 is 0.03 units, but an alternative higher cut-off may be used (or in addition, see below). The aim is to give recommendations on the characteristic/s which are most likely to provide significant health utility from a CI.

## 4.1 Statistics

### 4.1.1 Sample Size

The decision of success/fail in significant impact of CI on HUI3 scores requires paired pre/post data in order to test the difference scores. Currently one centre has good follow-up, ZA-01, and overall a high number of patients with 161 at baseline and 117 at 1 year as of December 2019. Thus approximately 110 datapoints are available.

### 4.1.2 Analyses

A logistic regression approach will be used to determine which factors may significantly influence gains in HUI3 scores.

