### Histogram of dat.w.temp\$hui.v3.score.multi.1 - dat.w.temp\$hui.v3.score.mul

The mean difference score is 0.149, with a confidence interval of ~0.1 to ~0.2. As stated above, 0.1 is generally considered to indicate a highly significant individual gain in HRQoL. Based on the histogram above, somewhat more than 50% of cases achieved a HUI3 gain of >0.1. An approximate cut-off representing 50% of cases is a good basis for a success/fail criterion for a logistic analysis (i.e. median gain in HUI3 for example). However, it may be useful to tune the criterion to improve the predictive performance of the model once initial results are obtained for gain = 0.1.

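### SAP section 4 models HUI3 gain only as success/fail near the median, with a cut-off that may be tuned later; an ordinal main model would usually keep more information and needs no cut-off

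*SAP*

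**What the plan says.** SAP section 4 sets the framing: "To differentiate from previous publication the approach will be to establish odds of improvement in HUI Mk III scores". Section 4.1.2 names the model: "A logistic regression approach will be used to determine which factors may significantly influence gains in HUI3 scores".

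Section 4.1.2.1 chooses the cut. It notes that 0.03 is the minimum important change, states an interest in changes of at least 0.1, and describes 0.1 as a large individual gain in quality of life. It reports that "somewhat more than 50% of cases achieved a HUI3 gain of >0.1" and adds that "An approximate cut-off representing 50% of cases is a good basis for a success/fail criterion for a logistic analysis", giving the median gain as an example. It then leaves the cut open: "it may be useful to tune the criterion to improve the predictive performance of the model once initial results are obtained". Section 4.1.5 plans univariate logistic models, multivariate ones if feasible, and again allows the threshold to be varied, for instance by ROC.

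On sample size, section 4.1.1 counts "161 at baseline and 117 at 1 year as of December 2019" at one centre and concludes: "Thus approximately 110 datapoints are available". Section 4.1.2.2 lists seven typical candidate factors, several of them with more than two categories.

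Section 4 contains no linear, ordinal or other model of the full gain. Section 1.3.2.2 does model HUI3 as a continuous score in a mixed model and permits covariates, but its hypothesis is age group by visit.

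**The concern.** HUI3 gain is a graded score. Cutting it at 0.1 treats a gain of 0.11 like one of 0.60, and a gain of 0.09 like a loss of 0.40. With about 110 patients and seven or more candidate factors, lost information reduces the chance of finding factors that matter, and the aim of section 4 is to recommend which characteristics go with a worthwhile gain.

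The second issue is that the main result depends on one cut-off, and the plan allows that cut-off to move after results are seen in order to improve prediction. Odds ratios and p-values at a cut chosen that way are hard to interpret.

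**Working it through.** **Inputs.** From SAP 4.1.2.1: mean gain 0.1490534, t = 5.9659, df = 132, 95% CI 0.09963 to 0.19847. From 4.1.1: n about 110. Assumed here, because section 4 gives none: two-sided 5% level, a binary factor split 50/50, and a true shift of 0.5 SD.

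**1. The plan's own figures reproduce.**
- SE = 0.1490534/5.9659 = 0.02498. SD of gain = 0.02498 × √133 = 0.288.
- The CI recomputes to 0.0996 to 0.1985, and p to 2.1e-08.
- With a normal gain, the share above 0.1 is 1 − Φ((0.1 − 0.149)/0.288) = 56.8%, in line with the plan's statement. The 0.1 cut is therefore near the median.

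**2. Information kept by a median cut** (f is the density of gain, σ its SD).
- Cut against linear: 4 f(median)² σ². Normal: 2/π = 0.637, a loss of 36%.
- Ordinal (rank-type) against linear: 12 σ² (∫f²)². Normal: 3/π = 0.955.
- Cut against ordinal: f(median)² / [3 (∫f²)²]. Normal: 0.637/0.955 = 0.667, a loss of 33%. Logistic, where proportional odds is exact: (1/4)² / [3 × (1/6)²] = 0.75, a loss of 25%.
- Against an ordinal analysis of 110 patients, the cut is worth about 110 × 0.667 = 73 patients (normal) or 110 × 0.75 = 83 (logistic).
- At 0.1 rather than the exact median, the loss against ordinal is 34% (normal) and 27% (logistic).

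**3. Power at n = 110** (55 per group). The shift is 0.5 × 0.288 = 0.144, so the group means are 0.077 and 0.221.
- Normal gains: the proportions above 0.1 are 0.468 and 0.663. Pooled SE is 0.0945 and unpooled SE 0.0927, so power for the cut = Φ((0.195 − 1.96 × 0.0945)/0.0927) = 54%. Ordinal: Φ(0.5 × √(55/2) × √0.955 − 1.96) = 73%.
- Logistic gains: the proportions are 0.464 and 0.682, and the same formulas (relative efficiency 1.097) give 64% for the cut and 78% for ordinal.
- Simulation, with the Wilcoxon test standing in for the proportional-odds score test, agrees within about two points: 53% to 55% against 72% to 73% (normal), and 63% to 65% against 77% to 79% (logistic).

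**4. Sensitivity to shape** (same set-up, 0.1 cut, cut against ordinal).
- t with 5 df: about 70% against 81%.
- Laplace: about 85% against 86%.
- An assumed three-cluster mixture (improved, unchanged, worse, in the proportions of Table 2 in SAP 4.1.2.3), with the factor changing the chance of improving: 62% against 59%, so the order reverses.

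**5. Sample size in the plan.** Section 4.1.1 gives about 110, with 117 patients at 1 year. The t-test has 132 + 1 = 133 pairs, and Table 2 also sums to 133 (72 improved, 46 unchanged, 15 worse in hearing category). These cannot all describe the same set. Relative losses do not depend on which n is right.

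**The case against.** The best defence is that section 4 asks a responder question. Its aim is to identify who is likely to obtain a significant gain, and section 4.1.2.1 gives a clinical reason for 0.1. A common odds ratio across all cuts answers a different question, so preferring it is partly a choice of estimand. This stands, and is why the 0.1 model should be kept. It does not protect the plan as written: the cut is also justified by its 50:50 split and may be moved to improve prediction, and a cut moved for that purpose no longer carries the clinical meaning of 0.1.

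The shape of the gains is also open. Section 4.1.2.3 says much of the HUI3 variation comes from the six-level hearing attribute, and 46 of 133 patients do not change category. Clustering is plausible, and step 4 shows that the advantage can shrink or reverse. This too stands.

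Section 1 does model HUI3 as a continuous score, and section 1.1 lists many of the same factors as possible predictors. That use is optional and centred on age, so it does not replace a predictor analysis in section 4.

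A reader might also infer that 110 is a hard ceiling. The documents do not support that: section 4.1.1 gives a count as of a date, and the protocol synopsis describes continuing collection.

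**Conclusion.** The concern holds in a conditional form. Section 4 relies on a single near-median cut of a graded score, has no full-scale model of gain, and lets the cut be tuned after results. Against an ordinal model the cost is about a quarter to a third of the information if gains are roughly logistic or normal, or about 14 to 18 points of power in the illustration. The 0.5 SD effect, the 50/50 factor and the distributions are assumptions, not figures from the documents.

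Three stronger readings are tempting and not supported:
- A flat 36% loss. That figure needs normal gains and a linear comparator, and the histogram was not available to us.
- That the cut has no scientific basis. The wish to differ from a previous publication explains the odds framing, but 0.1 has a stated clinical reason.
- That real predictors will be missed. The effect size is assumed, and the ordinal model itself misses about 27% (normal) or 21% (logistic) in the same illustration.

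Dependence on a tuned cut-off does not rest on any distributional assumption and is the firmer part of the point.

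**What to change.** Make a proportional-odds (cumulative logit) regression of the full visit-1 HUI3 gain the main section 4 model, reporting one odds ratio of greater improvement per factor. This keeps the odds-of-improvement framing, and the main result cannot depend on a cut-off picked after seeing data. Keep the logistic model as a secondary responder analysis with 0.1 fixed in advance; it answers the threshold question directly. Add linear regression with robust standard errors as a check. State in section 4.1.1 which patients are analysed, and reconcile 110 with 133.

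The cost is a few lines of R, no new data, and rewording of sections 4.1.2, 4.1.2.1, 4.1.2.2 and 4.1.5, which are written around success/fail. The downside is that the ordinal odds ratio is a common one across all cuts, not the odds of exceeding 0.1, and the proportional-odds assumption must be checked. Keeping the 0.1 model does not by itself deal with a violation, so the plan should say what will be reported if the check fails.

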#### 4.1.2.1 Pass/Fail Criteria

[figure not shown]
The minimum clinically important change/difference in HUI3 is 0.03 units. For HUI3 this change is very small and larger mean differences are typically observed. As such for these analyses we are interested in differences/changes of at least 0.1 units. Below is summarised the simple paired comparison of baseline versus 1-year HUI3 scores:

```
> t.test(dat.w.temp$hui.v3.score.multi.1,dat.w.temp$hui.v3.score.multi.0, p
aired=TRUE)
```

```
Paired t-test
```

```
data: dat.w.temp$hui.v3.score.multi.1 and dat.w.temp$hui.v3.score.multi.0
t = 5.9659, df = 132, p-value = 2.105e-08
alternative hypothesis: true difference in means is not equal to 0
95 percent confidence interval:
 0.09963182 0.19847490
sample estimates:
mean of the differences
      0.1490534
```

### Histogram of dat.w.temp\$hui.v3.score.multi.1 - dat.w.temp\$hui.v3.score.mul

The mean difference score is 0.149, with a confidence interval of ~0.1 to ~0.2. As stated above, 0.1 is generally considered to indicate a highly significant individual gain in HRQoL. Based on the histogram above, somewhat more than 50% of cases achieved a HUI3 gain of >0.1. An approximate cut-off representing 50% of cases is a good basis for a success/fail criterion for a logistic analysis (i.e. median gain in HUI3 for example). However, it may be useful to tune the criterion to improve the predictive performance of the model once initial results are obtained for gain = 0.1.

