#### 4.1.2.2 Primary Hypothesis and Analysis

Once the criterion for “significant gain” in HUI3 is defined, the baseline characteristics of those meeting and not meeting the criterion can be compared. Then it can be hypothesised that those characteristics which are divergent for the group may influence significant gain in HUI3 scores.

Typical factors to consider are etiology, age, duration of hearing loss/deafness, onset of hearing loss, use of hearing aids, tinnitus status, and dizziness status. There are too many etiology categories compared to the total N of subjects so they will be grouped as in Table 1.

For the effects of age, continuous variable or range groups may be evaluated (i.e. approximate ABS age as in Section 1 above will be used unless sample sizes are too small).

Onset of deafness in childhood, or “congenital” deafness may be calculated from age and duration of hearing loss. In consultation with the centre, “pre-linguistic” onset of deafness is

[figure not shown]
defined as <10 years of age. Arguably “congenital” deafness should be limited to ages <2 (for the purposes of identification). The other defined onsets are progressive and sudden HL.

Table 1. Etiologies (implanted ear) at baseline grouped for ZA-01.

Familial	7
Vestibular ( Large vestibular aqueduct Menieres syndrome)	8
Meningitis	8
Viral, (measles and mumps rubella)	9
Ototoxic drugs	11
Middle ear: Cholesteatoma, Congenital atresia, Otosclerosis	15
Other	27
Unknown	75

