#### 4.1.5 Presentation of data

The report will conform to a conventional format with data completeness and population summaries (such as demographics).

Summary statistics will be provided for baseline characteristics for those patients reaching the 0.1 HUI3 gain at visit 1, and those who did not. Similarly, for those with baseline HUI hearing attribute categories  $\leq 3$  and those  $>3$ .

Univariate logistic models will be produced with estimated odds ratios and p-values will be presented. If feasible, multivariate logistic models will be produced. In addition, the predictive

capability of the model can be tested, and/or the threshold criterion varied (e.g. via RoC) to obtain higher predictive power.

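### SAP 4.1.2.1 lets the HUI3-gain cut-off for success be re-chosen after the results at 0.1 are seen; if that is done, the p-values, odds ratios and apparent AUC are optimistic

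*SAP*

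**What the plan says.** SAP section 4 aims to recommend which patient characteristics make a worthwhile utility gain from a cochlear implant most likely. The method is logistic regression on success or failure in HUI3 gain, so the gain cut-off defines the outcome.

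The cut-off is left open in several places:

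- Section 4 gives 0.03 as the minimum clinically important change and adds that "an alternative higher cut-off may be used (or in addition, see below").
- Section 4.1.2.1 moves to 0.1: "As such for these analyses we are interested in differences/changes of at least 0.1 units".
- The text under the histogram in 4.1.2.1 adds the median as a candidate: "An approximate cut-off representing 50% of cases is a good basis for a success/fail criterion for a logistic analysis". It then says it may be useful to "tune the criterion to improve the predictive performance of the model once initial results are obtained for gain = 0.1".

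Section 4.1.2.2 lists seven typical factors: etiology, age, duration of loss, onset, hearing aid use, tinnitus and dizziness. It compares the two outcome groups on them: "Then it can be hypothesised that those characteristics which are divergent for the group may influence significant gain in HUI3 scores". Section 4.1.5 sets the output: "Univariate logistic models will be produced with estimated odds ratios and p-values will be presented". Multivariable models follow if feasible. The same section says predictive capability can be tested and a threshold varied, for example by ROC, to raise predictive power. It ties the descriptive baseline summaries to the 0.1 gain, but not the logistic models.

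**The concern.** Choosing a threshold on the predicted probability is routine. This is different: the quantity that may be moved is the amount of HUI3 gain that counts as success. Moving it because the model then performs better fits the outcome to the predictors.

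Section 4 has no list of permitted cut-offs, no selection rule, no requirement to show the 0.1 result beside a tuned one, and no hold-out, resampling or alpha correction. Because tuning is allowed by the plan it would not be a deviation, and the SAP introduction says deviations need not be reported in any case. A reader of the publication could not tell how many cut-offs had been tried.

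The output is meant to guide recommendations on candidates. A factor that stands out by chance at one convenient cut-off could become such a recommendation, with too small a p-value and too large an odds ratio.

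**Working it through.** **1. Reproduce the SAP's own figure.** Section 4.1.2.1 prints "t = 5.9659, df = 132, p-value = 2.105e-08" with mean difference 0.1490534.

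- SE = mean / t = 0.1490534 / 5.9659 = 0.02498.
- Pairs = df + 1 = 133. SD of gain = 0.02498 × √133 = 0.288.
- 95% CI = 0.14905 ± t(0.975, 132) × 0.02498 = 0.14905 ± 0.04942 = 0.0996 to 0.1985; two-sided p = 2.10e-08. Both agree with the SAP.
- If gains are normal, 56.8% exceed 0.1, which fits the SAP's remark that somewhat more than half do.

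**2. Number of patients.** Section 4.1.1 says of centre ZA-01, with 117 one-year records: "Thus approximately 110 datapoints are available". The t-test has 133 pairs, and Table 2 of section 4.1.2.3 sums to 37 + 47 + 2 + 40 + 2 + 5 = 133. Since 133 exceeds 117, the two figures cannot describe the same set. Both n = 110 and n = 133 were therefore run.

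**3. Null simulation of the option.** No factor is related to gain. Gain has mean 0.149 and SD 0.288 (normal; heavy-tailed in one set of assumptions). There are seven factors; apart from etiology, their distributions are assumed and varied. Each factor has a univariate likelihood-ratio test at 5% (section 4 states no alpha; this is assumed from SAP section 1 and protocol 12.1). Tuned means the cut-off with the highest apparent multivariable AUC. The choices are:

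- fixed: 0.1;
- two: 0.03 and 0.1;
- three: those and a median taken as about 0.15;
- grid: 13 values (0.03 to 0.25 in steps of 0.02, plus 0.10).

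The main scenarios use 1,200 data sets each.

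| Model | n | At least one p<0.05: fixed / two / three / grid | Apparent AUC: fixed / grid |
|---|---|---|---|
| 17 coefficients | 110 | 36 / 45 / 47 / 58% | 0.728 / 0.768 |
| 17 coefficients | 133 | 33 / 42 / 45 / 57% | 0.705 / 0.741 |
| 7 coefficients | 110 | 32 / 40 / 44 / 57% | 0.641 / 0.679 |
| 7 coefficients | 133 | 34 / 40 / 45 / 60% | 0.629 / 0.664 |

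Six more scenarios (700 data sets each) bring the ranges to 30-37%, 40-45%, 44-49% and 54-63%. Monte Carlo SE is about 1.4-1.9 points. The fixed column is close to 1 − 0.95^7 = 30%, the value for seven independent tests. For one binary factor on the grid, the error rate goes from about 5% to 8-11% and its typical null odds ratio from 1.38 to 1.48 (n = 110).

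**4. Second simulation, tuning on one factor's own AUC.** This used 3,000 runs per setting, normal gains and seven unrelated factors (three continuous, four binary). Results are for one continuous factor; the odds ratio is per SD and its true value is 1. The AUC is that of the seven-factor model, with the cut-off tuned on that model.

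| Cut-offs | n | Type I error | Mean odds ratio | Seven-factor AUC |
|---|---|---|---|---|
| 0.10, 0.125, 0.149 | 110 | 4.7 → 7.3% | 1.18 → 1.22 | 0.642 → 0.656 |
| 0.03, 0.10, 0.149 | 110 | 4.3 → 8.6% | 1.17 → 1.25 | 0.640 → 0.663 |
| 8 values, 0.03-0.20 | 110 | 4.1 → 12.8% | 1.17 → 1.29 | 0.640 → 0.673 |
| 8 values, 0.03-0.20 | 133 | 4.9 → 12.3% | 1.16 → 1.26 | 0.629 → 0.658 |
| 11 values, 0-0.30 | 110 | 5.1 → 17.0% | 1.18 → 1.34 | 0.642 → 0.688 |

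Single-factor rates are higher here than in step 3 because the cut-off is chosen on that factor's own AUC.

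**5. Narrow case.** When the choice is only between 0.1 and the median (taken as 0.12 or as the sample median), the chance of at least one significant null factor goes from 33-36% to 35-42%. The AUC rises by about 0.01.

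**6. What validation recovers at fixed 0.1** (300 null data sets, true AUC 0.50). Bootstrap optimism correction leaves 0.575, 0.564, 0.543 and 0.544 in the four main scenarios. One round of 10-fold cross-validation gives 0.499, 0.497, 0.502 and 0.507.

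**The case against.** The strongest reply is that the step is optional and the publication is retrospective and close to hypothesis-generating. Section 4.1.2.2 places the criterion before the group comparison, and 4.1.5 keeps the descriptive tables at 0.1 and mentions testing predictive capability. The 13-value grid appears nowhere in the SAP. Section 4.1.2.1 itself calls 0.03 very small, and the median must lie above 0.1, so the realistic choice may be only between 0.1 and a nearby value. Multivariable models are produced only if feasible, so tuning on a multivariable AUC is one reading of predictive performance.

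Much of this stands as to size. The grid figures are an assumed upper case, and the narrow case adds only a few points. Most of the apparent AUC above 0.50, and about a one-in-three chance of a false factor, exist at a fixed 0.1 and come from overfitting and from testing seven factors.

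The objection does not remove the point. The direction is the same on every set of cut-offs tried, and the plan sets no limit on the search. Section 4 does not label the analysis exploratory: 4.1.2.2 is headed as the primary hypothesis and analysis. The 4.1.5 remark on ROC can be read as the ordinary probability threshold, but the sentence in 4.1.2.1 clearly concerns the HUI3-gain criterion. The 133 pairs may be a pooled set, since the figure in 4.1.2.3 is described as covering all CI subjects; the SAP should say so. The conclusion is the same at either number.

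**Conclusion.** The concern holds. As written, the SAP allows the outcome definition to be chosen on the results. If the option is used, the p-values are not valid at their nominal level, and the odds ratios and apparent AUC are too large.

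The size depends on how widely the cut-off is searched. From a base of 30-37%, the chance of at least one false factor becomes 44-49% with the three cut-offs section 4 names (median taken as about 0.15) and 54-63% on the assumed 13-value grid. In the narrow case it moves only from 33-36% to 35-42%. Tuning itself adds about 0.01-0.05 to the apparent AUC. These figures rest on no true effects, an SD of gain of 0.288, a 5% level and assumed factor distributions.

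This should be corrected before modelling. It is a defect in one planned publication, conditional on the option being used and cheap to close.

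**What to change.** - In 4.1.2.1, name a HUI3 gain of at least 0.1 as the single primary definition of success before modelling, and delete the tuning sentence. The choice is not blind, because the gain distribution has already been inspected, but it uses the SAP's own value.
- Name 0.03 and a linear model of continuous gain as sensitivity analyses. Report the 0.1 result beside every other cut-off examined.
- In 4.1.5, state that any ROC threshold refers to the predicted probability, not to the HUI3-gain cut-off.
- Report an internally validated AUC with any factor selection repeated in each resample. Repeated 10-fold cross-validation is the better choice here, since bootstrap correction left 0.54-0.58 under the null.
- Label the univariate p-values exploratory, because fixing the cut-off does not remove the multiplicity of seven factors. Formal adjustment is optional.
- State whether the analysis set is the roughly 110 pairs of 4.1.1 or the 133 of the t-test.

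The cost is SAP wording and a short resampling step, with no new data. The headline AUC and the number of significant factors may fall, and a cut-off that predicts better than 0.1 could be reported only as a sensitivity result.
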